Generalized estimating equations (GEE) will be used to examine the difference between intervention and waitlist groups in change from baseline to 12 and to 24 weeks for QOL (primary outcome). Time, group and the group by time interaction will be included in the model. We will also calculate Hedges' g for differences in change over time between the groups in change in primary outcomes. Hedges' g is recommended over Cohen's d' to correct of an upward bias in small sample sizes.⁸⁵ The effect size associated with the variables will be compared to established clinically significant improvement reported in the literature, rather than placing emphasis on statistical significance.

b. Secondary outcome variables.

Generalized estimating equations (GEE) will be used to examine the difference between intervention and waitlist groups in change from baseline to 12 and to 24 weeks for self-efficacy and HRV (secondary outcomes) using a similar approach (as described for primary outcome).

In addition, the correlation between the change in the mechanisms and change in primary outcomes will be examined. We will also examine cost of the intervention.

Mixed Methods Analysis - Qualitative analysis and joint displays will be used to compare those with improvement in quantitative outcomes after the intervention to those who did not have improvement to elucidate unmeasured or unpowered change as reported by participants. This mixed methods analytic approach to intervention evaluation maximizes what we will learn from the pilot by increasing understanding of context, responsiveness to ethnically and culturally diverse populations and how implementation influences outcomes. Thus, the development and testing of the HEROIC intervention will address preventive health behaviors of HF caregivers, using rigorous methods to

promote inclusivity and tailor the intervention to caregiver needs to decrease caregiver burden and improve quality of life.

c. Statistical plan including sample size justification and interim data analysis.

Sample Size:

Aim 1) For our open-label pilot we will include 5 caregivers to test intervention components, feasibility, acceptability, delivery and communication.

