Aim 2) As a pilot study, the analyses will not have adequate power to detect significant differences. Therefore, initial effect sizes, rather than statistical significance, will be examined for evidence of the effectiveness of the intervention. With a target sample size of 44, 22 in the waitlist control and 22 in the intervention, we will be able to gauge an initial estimate of the effect size associated with the intervention as compared to usual care for caregivers. Waitlist control groups are used to first provide an untreated comparison and second to allow wait-listed participants an opportunity to receive the intervention at a later date. ⁸⁷ This is especially appropriate given that very few services are currently offered to HF caregivers. We will also conduct debriefing interviews with all participants following the trial. To account for an estimated 20% attrition, we will recruit a total of 49 to the trial with the goal of 44 participants completing the study.

Understanding the factors that predict which intervention components are successfully implemented and for which participant subgroups will be critical for fine-tuning this multicomponent intervention for future proposals that will extend efficacy examinations and effect modification analyses. Acceptability of the intervention will be examined in multiple ways. We will examine percentages of people who stayed in each arm of the study and conduct numerous descriptive correlational analyses of the association between the intervention compliance and other variables. These analyses will quantify intervention implementation by demographic and participant health variables. Analyses that utilize the post-randomization data (e.g., treatment compliance) ⁴⁰⁻⁴³ will be evaluated in supplementary analyses. We will distinguish non-compliance with intervention from attrition or loss to follow-up, i.e., missing data. We will also use the participant satisfaction data to examine acceptability of the intervention.

d. Early stopping rules.

As this is a low-risk behavioral intervention pilot, we have not defined any early stopping rules.

8. Risks

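### The outcomes are to be analysed by unweighted GEE with no stated working correlation or missing-data assumption and 20% attrition expected; a baseline-using analysis valid under missing at random would modestly protect the pilot's effect estimate

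*Combined protocol and SAP*

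**What the plan says.** Section 7 (Study Statistics), Aim 2 item a, states for QOL: "Generalized estimating equations (GEE) will be used to examine the difference between intervention and waitlist groups". The contrast is change from baseline to 12 and to 24 weeks. The terms are given as "Time, group and the group by time interaction will be included in the model". Item b extends the method "for self-efficacy and HRV (secondary outcomes) using a similar approach (as described for primary outcome". Hedges' g is also to be calculated on change, with no word on whether it comes from the model or from the observed change scores.

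Item c gives the attrition allowance: "To account for an estimated 20% attrition, we will recruit a total of 49", with 44 expected to complete. The only remark on missing data is "We will distinguish non-compliance with intervention from attrition or loss to follow-up, i.e., missing data". That is a definition and does not say how missing data are handled.

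Nothing states the working correlation, the missing-data assumption, any weighting or imputation, or a small-sample variance correction. Adjustment for baseline differences is foreseen at the start of Section 7, but only where the groups are found to differ, and the one sensitivity analysis there concerns that imbalance. The spousal stratum used in randomisation (Section 4, Randomization) is not in the model.

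**The concern.** Unweighted GEE is in general consistent only if dropout is unrelated to the outcomes, given the covariates in the model. A likelihood-based repeated-measures model needs the weaker condition that dropout may depend on observed scores (missing at random, MAR). Before week 12 one arm has nurse sessions and calls while the other has usual care and monthly postcards, so it is plausible, though not shown, that the scores of those who leave differ by arm.

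The plan presents an initial effect size, not a significance test, as the trial's product, to be set against clinically significant improvement reported in the literature. A shift of 0.1 SD or more from dropout alone would go straight into that comparison. Because the working correlation is open, an analyst could use independence, the choice most exposed to this, and still comply with the plan.

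**Working it through.** **1. Attrition input.** The stated 20% does not reproduce the stated numbers: 44/(1 − 0.20) = 55, 44 × 1.20 = 52.8, and 49 × 0.80 = 39.2 completers. Going from 49 to 44 is a loss of 5/49 = 10.2%. The allowance also concerns completing the study, which runs to week 24. I therefore take 10% and 20% lost by week 12 as the range. (The mismatch is a separate point.)

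**2. Assumptions not in the documents.** Outcome SD 1; baseline to week-12 correlation ρ = 0.5 to 0.7; log-odds of dropout changing by 1 per SD of baseline score in one arm, with dropout at the same rate in the other arm either random or dependent in the opposite direction.

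**3. Independence GEE by formula.** With time, group and interaction the mean model is saturated, so independence GEE returns the observed mean in each arm at each visit. The baseline mean uses everyone; the week-12 mean uses those who stayed. Let δ be the shift in mean baseline score among those who stayed:

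δ = E[x(1 − p(x))]/(1 − d), for standard normal x, dropout probability p(x) and overall dropout d.

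Numerical integration gives δ = 0.091 at d = 0.10 and 0.173 at d = 0.20. The week-12 mean shifts by ρδ and the baseline mean does not, so the contrast is biased by ρδ, or 2ρδ if the arms select in opposite directions.

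| Lost by week 12 | One arm selective, ρδ | Opposite directions, 2ρδ |
|---|---|---|
| 10% | 0.5 × 0.091 = 0.05 to 0.7 × 0.091 = 0.06 | 0.09 to 0.13 |
| 20% | 0.5 × 0.173 = 0.09 to 0.7 × 0.173 = 0.12 | 0.17 to 0.24 |

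If both arms select in the same way, the shifts cancel. If low scorers leave the waitlist, the effect is understated; if they leave the intervention arm, it is overstated.

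**4. Hedges' g on observed change.** Among those who stayed, mean change shifts by ρδ − δ = −(1 − ρ)δ, the opposite sign. At 20% lost this is 0.3 × 0.173 = 0.05 to 0.5 × 0.173 = 0.09 SD, doubled to 0.10 to 0.17 for opposite directions. The model contrast and g could then disagree because of dropout alone.

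**5. Other working correlations, by simulation.** Absolute week-12 bias in SD, 60,000 per arm, correlations 0.6/0.4/0.6, Monte Carlo error about 0.005 to 0.01:

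| Dropout | Lost by week 12 | GEE independence | GEE exchangeable | GEE unstructured | Likelihood mixed model |
|---|---|---|---|---|---|
| MAR, same in both arms | 10% or 20% | ≤ 0.01 | ≤ 0.01 | ≤ 0.01 | ≤ 0.01 |
| MAR, differs by arm | 10% | 0.048 | 0.001 | 0.005 | 0.006 |
| MAR, opposite by arm | 10% | 0.110 | 0.016 | 0.004 | 0.001 |
| MAR, differs by arm | 20% | 0.112 | 0.022 | 0.012 | 0.008 |
| MAR, opposite by arm | 20% | 0.214 | 0.041 | 0.023 | 0.009 |
| Not at random, differs by arm | 10% | 0.086 | 0.059 | 0.055 | 0.055 |
| Not at random, differs by arm | 20% | 0.165 | 0.111 | 0.104 | 0.105 |

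A repeat of the MAR cases with 400,000 per arm and four correlation sets gave at most 0.03 for exchangeable and 0.02 for unstructured GEE, both in the opposite-direction 20% case. Independence GEE with baseline as a covariate was biased by at most 0.026 SD in a separate run of comparable MAR scenarios.

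**6. Sampling error for scale.** At 24 per arm the simulated SD of the week-12 estimate was 0.25 to 0.29 for every method. At 22 per arm and an assumed effect of 0.5, the 95% half-width for a standardised difference is 1.96 × √(2/22 + 0.5²/(2 × 44)) = 0.60.

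**The case against.** The strongest reply is that the gap lies in the unstated working correlation, not in GEE. For a continuous outcome with a non-independence correlation, GEE comes close to the likelihood result, and adding baseline as a covariate does most of the work even under independence. That stands, and it is why retaining GEE is an acceptable alternative below.

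It is also fair that the bias needs dropout to depend on scores differently by arm, and that the larger figures need opposite directions. The documents give no evidence of either pattern, and putting all 20% before week 12 is the pessimistic end. The trial disclaims power, and its sampling error exceeds the bias. All of this stands and limits the weight of the point.

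A reader might go further and infer that GEE is an error here, that dropout in this trial will be selective, or that a mixed model removes the bias at no cost. The documents do not support the first two. The third fails on the calculations: when dropout depends on the unobserved current score, the mixed model is as biased as unstructured GEE (0.06 to 0.11 SD). It also brings covariance and distributional assumptions, gives up the robustness of the sandwich variance, and at this size needs a small-sample degrees-of-freedom method.

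What the reply does not answer is that the plan fixes none of the choices that would keep GEE safe. Baseline adjustment is conditional on finding a difference, and the source of Hedges' g is open.

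**Conclusion.** The point holds as a modest improvement. As written, the plan permits an analysis whose week-12 contrast could be biased by about 0.05 to 0.12 SD, or 0.09 to 0.24 SD in the opposite-direction case. This requires dropout of 10 to 20% by week 12 that depends on earlier scores differently by arm, and an independence working correlation. Both conditions are assumptions. Without the first the bias is about zero. With an exchangeable or unstructured correlation it is usually at most 0.02 SD, and 0.03 to 0.04 SD in the most extreme case simulated. The protection applies under MAR only. The bias is smaller than the sampling error of a trial this size, but it is avoidable and affects the quantity the pilot is meant to deliver.

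**What to change.** In Section 7, Aim 2, for the continuous outcomes:

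- Use a repeated-measures mixed model fitted by REML, with unstructured covariance and a small-sample degrees-of-freedom correction (for example Kenward-Roger), including all randomised participants with any outcome data.
- Include visit, group, group-by-visit and the spousal stratum. Use baseline either as a covariate or as a first outcome with equal means across arms; the latter lets caregivers lost before week 12 still contribute.
- Name the week-12 group difference as the primary contrast, and derive Hedges' g from it, not from observed change scores.
- If GEE is kept, adjust for baseline and stratum regardless of observed imbalance, fix a non-independence working correlation, and use a small-sample-corrected variance.
- State the missing-data assumption and add a simple sensitivity analysis for data missing not at random, such as shifting the unobserved scores by a range of amounts in each arm.

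The cost is SAP wording and standard software; baseline and stratum are already collected. The downside is a covariance and distributional assumption, small with three visits. No loss of precision appeared in the simulations. The change does not address the exclusion of caregivers whose care recipient dies (Section 4, Death of the Patient), which needs its own decision.

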| Week 10 | Discuss how caregiver will involve social support in next goals |
| | Walking meeting (if virtual: suggest participant take a walk during call) |
| Phone Check-in | Review/edit purpose statement |
| Week 12 | Assess goal attainment and strategies to achieve goal |
| | Walking meeting (suggest participant take a walk during call) |
| Data Collection Visit | Heartrate Variability Measurement |
| Week 12 | Survey |
| Data Collection Visit | Heartrate Variability Measurement |

Week 24 Survey

Death of the Patient: If the patient/care recipient of the enrolled caregiver/study participant dies during the study, we will send a sympathy card. In that communication, we will ask the caregiver if they would like to participate a modified version of the intervention for bereavement: 1-3 visits (scheduled every other week) with a nurse for bereavement support within two months of the death of the care recipient. Additional instrumental support resources will be suggested such as grief support groups, referral to Roberta's House and bereavement resources for tasks to complete after someone you love dies. If the caregiver chooses to discontinue their participation, we will discontinue study contact and data collection. Data from caregivers whose care recipient dies will be excluded from analysis of primary and secondary outcomes.

Research Variables and Measurement

We chose measures (Table 2) based on previous RCT experience of mentors as well as those that met the following criteria: 1) possess known reliability and validity with ethnically diverse samples; 2) are sensitive to change from an intervention; 3) have clinical relevance; 4) Common Data Elements to connect this work with the broader literature and 5) represent objective as well as subjective indicators of the domains we seek to impact. Finally, we sought to achieve a balance between psychometric quality and practical considerations such as respondent burden. All instruments with the exception of demographics will be measured at baseline, 12 and 24 weeks. Patient characteristics will be obtained from chart review.

^{*} Waitlist control group will begin intervention at week 12.

Table 4: Constructs, Instruments and Reliability

| Theoretical Construct | Instruments and variables | Cronbach's alpha | | | |
|--|--|---------------------|--|--|--|
| | Contextual Factors | | | | |
| | 1)How well does the amount of money you have take care | | | | |

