| Financial Strain | of your needs? 2)In general, how do your finances usually | - | | | |
| | work out at the end of the month? | | | | |
| Social Support | ENRICHED Social Support Instrument ⁶⁹ | 0.88 | | | |
| | Caregiver Characteristics | | | | |
| Demographics | Age, Race, Gender | - | | | |
| Depression | Patient Health Questionnaire (PHQ-8) ⁷⁰ | 0.86 | | | |
| Perceived Stress | Perceived Stress Scale ⁷¹ | 0.82 | | | |
| Co-morbidities | Charlson Comorbidity Index ^{72,73} | 0.81 | | | |
| | Patient Characteristics | | | | |
| Functional Status | New York Heart Association Class (chart review) | - | | | |
| Cognition | Mini-mental status exam (chart review) | - | | | |
| Co-morbidities | Charlson Comorbidity Index (chart review) ^{72,73} | 0.81 | | | |
| | Katz independence in activities of daily living ⁷⁴ (caregiver | | | | |
| Independence of Care | report) | 0.84 | | | |
| Recipient | Lawton instrumental activities of daily living ⁷⁵ (caregiver | 0.85 | | | |
| | report) | | | | |
| | Potential Mechanisms | | | | |
| Self-efficacy | Coping self-efficacy ⁷⁶ | 0.91 | | | |
| Resilience | Heart rate variability | - | | | |
| | Caregiver Outcomes | | | | |
| Goal Attainment: Preventive Health Behaviors | Goal Attainment Scaling ⁷⁷ | 0.91 | | | |
| C . D 1 | Oberst Caregiver Burden Scale ⁷⁸ | 0.00 | | | |
| Caregiver Burden | 2 domains: time caregiving and task difficulty | 0.90 | | | |
| | Modified Caregiver Strain Index ^{79,80} | 0.86 | | | |
| Quality of Life | NeuroQOL | 0.85 | | | |
| Quality of Life | RAND 36-Item Short Form Survey | | | | |
| | 1) "Since our last contact, were you seen at an emergency | | | | |
| Health care utilization | room or a medical facility (e.g., Urgent care) for outpatient | | | | |
| | treatment?" | - | | | |
| | 2) "Since our last contact, were you hospitalized, or did | | | | |
| | you stay in a hospital observation unit for any reason?"* | | | | |
| Fatigue | PROMIS Fatigue – Short Form | | | | |
| Family Function | Family Assessment Device - Global/General Functioning | | | | |
| | Scale | | | | |

^{*}adapted from the Atherosclerosis Risk in Communities (ARIC) study annual follow-up questionnaire for healthcare utilization

Data collection and management:

Data Collection:

1) Questionnaires - Baseline, 12 and 24-week data will be collected by research assistants masked to treatment assignment. All data will be entered into RedCap.⁸¹

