- 6) Live within a 1.5 hour driving radius of the Johns Hopkins Hospital

Exclusion Criteria:

- 1) Caregivers with cognitive impairment using the six-item screener will be excluded. Severe Cognitive Impairment would make active participation in interviews and survey completion very difficult.
- 2) Non-English speakers will be excluded. Non-English speakers may have unknown needs that cannot be addressed with this intervention.
- 3) Caregivers with terminal diagnosis will be excluded as goal setting at end of life may be different than without a terminal diagnosis.

4) Caregivers who consented to IRB00203584 and participated in at least one intervention visit. These participants have received components of the intervention.

6. Drugs/ Substances/ Devices

N/A

7. Study Statistics

Exploratory and descriptive analysis will be completed for all study variables. Variables will be examined for normality and examined with means and standard deviations or medians and interquartile ranges accordingly. Baseline characteristics comparing the two groups (waitlist vs. immediate intervention) will be assessed. Any differences between the groups will be adjusted for further analysis. The significance level will be set at 0.05. Sensitivity analyses will be conducted adjusting for variables on which the group differ and compared to the pattern of results in the main analyses.

Analysis Plan:

Qualitative Analysis (Aims 1 and 3) - A qualitative descriptive analysis approach will be applied to data analysis of semi-structured interviews. 82,83 The codebook will be adjusted as needed. Similar codes will then be grouped into categories/themes that express the latent idea of grouped codes which will be used to refine the intervention protocol.

Aim 1 – In addition to qualitative analysis, descriptive analysis will be used to examine all quantitative data. Joint displays will be used to provide a structure to discuss the integrated quantitative and qualitative analysis and assist the study team in making changes to intervention components and overall protocol to improve feasibility and acceptability.⁸⁴

Aim 2 -

a. Primary outcome variable.

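### The planned QOL model uses the baseline value only through change, which usually costs precision in the pilot's effect estimate; adjustment for chance imbalance should be a sensitivity analysis only

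*Combined protocol and SAP*

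**What the plan says.** Section 7, Aim 2 a, uses GEE to compare the arms on "change from baseline to 12 and to 24 weeks for QOL (primary outcome") and specifies the model in one sentence: "Time, group and the group by time interaction will be included in the model". Part b applies a similar approach to self-efficacy and HRV. Neither part names a baseline covariate, a common-baseline constraint or the randomisation stratum (spousal versus non-spousal caregiver; section 4, Randomization). Baseline QOL will be available: "All instruments with the exception of demographics will be measured at baseline, 12 and 24 weeks" (section 4, Research Variables and Measurement).

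The effect size is Hedges' g for the between-arm difference in change, chosen because "Hedges' g is recommended over Cohen's d' to correct of an upward bias in small sample sizes". Its denominator is not named and no confidence interval is planned. Section 7 c, Aim 2, says what the pilot is meant to deliver: "Therefore, initial effect sizes, rather than statistical significance, will be examined for evidence of the effectiveness of the intervention".

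On baseline imbalance, the opening paragraph of section 7 says "Any differences between the groups will be adjusted for further analysis" and, two sentences later, "Sensitivity analyses will be conducted adjusting for variables on which the group differ and compared to the pattern of results in the main analyses".

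**The concern.** A difference in change fixes the coefficient on baseline at 1. When baseline and follow-up values are only moderately correlated, that subtracts too much and adds baseline noise to the estimate. A fitted baseline slope, or a model that gives both arms one baseline mean (which randomisation justifies), avoids most of that noise with data the trial already collects. The plan disclaims power and will set its effect size against clinically significant improvement from the literature, so the precision and scale of that one estimate are what is at stake.

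The two sentences on imbalance raise a smaller issue. Read literally, the first lets covariates enter the main model after the baseline comparison has been seen, with no rule for what counts as a difference. The second treats the same adjustment as a check on the main analyses.

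**Working it through.** **Inputs.** 22 per arm complete, 49 randomised and 20% attrition (section 7 c). The plan states no precision figure to reproduce. At 20% loss, 49 leaves 49 × 0.8 = 39.2 participants, not 44, so both cases are shown. Assumed, because the documents do not give them: baseline SD of 1, follow-up SD of k (first k = 1), baseline-to-12-week correlation r of 0.3 to 0.8, loss at random.

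**What the planned model estimates.** In GEE fits to simulated complete data, the 12-week interaction equalled the raw difference in mean change (0.3143 with independence and 0.2655 with exchangeable working correlation, each matching exactly). With 20% loss the two are close but not identical (median gap 0.02 to 0.07 SD).

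**Equal SDs, 22 per arm.** Variance of the 12-week difference:
- change: 2(1−r) × 2/22
- baseline-adjusted: (1−r²) × 2/22
- large-sample ratio: (1−r²) / [2(1−r)] = (1+r)/2

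Estimating the slope costs a factor of about 1 + 1/(44−4) = 1.025. Half-widths are the standard error times a t quantile of about 2.02, with that factor included for the adjusted analysis. For example, at r = 0.5 the change analysis gives √(1.0 × 2/22) = 0.302 and 2.02 × 0.302 ≈ 0.61.

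| r | (1+r)/2 | × 1.025 | 95% half-width, change | 95% half-width, adjusted |
|---|---|---|---|---|
| 0.3 | 0.65 | 0.67 | 0.72 | 0.59 |
| 0.5 | 0.75 | 0.77 | 0.61 | 0.53 |
| 0.7 | 0.85 | 0.87 | 0.47 | 0.44 |
| 0.8 | 0.90 | 0.92 | 0.385 | 0.370 |

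Two simulations of the GEE models gave variance ratios of 0.67, 0.77, 0.87, 0.93 and of about 0.70, 0.80, 0.90, 0.95. Together they give the reduction of roughly 33% to 5%. Put as sample size, a change analysis needs 44 ÷ (1+r)/2, or about 68, 59, 52 and 49 completers, to match the adjusted analysis in 44 before the slope penalty.

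**49 randomised, 20% lost.** Adjusting follow-up for baseline gave ratios of 0.73, 0.82, 0.91, 0.95 in one simulation. In the other, at r = 0.3, 0.5 and 0.8, it gave 0.72, 0.83, 0.94, and the common-baseline-mean model gave 0.70, 0.81, 0.92.

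**Unequal SDs.** The large-sample ratio becomes k²(1−r²) / (1 + k² − 2kr).
- k = 1.2: 1.3104/1.72 = 0.76; 1.08/1.24 = 0.87; 0.7344/0.76 = 0.97; 0.5184/0.52 = 0.997. Times 1.025 these are 0.78, 0.89, 0.99, 1.02. Simulation with 22 per arm gave about 0.80, 0.93, 1.02, 1.05.
- k = 0.8: 0.5824/1.16 = 0.50; 0.48/0.84 = 0.57; 0.3264/0.52 = 0.63; 0.2304/0.36 = 0.64.

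A common-baseline GEE with exchangeable working correlation and one variance for all visits uses a baseline coefficient near r rather than the best value kr. At k = 1.2 and r = 0.8 its ratio is (1.44 + 0.64 − 2 × 1.2 × 0.64)/0.52 = 0.544/0.52 = 1.05.

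**Scale of Hedges' g.** A true difference of 0.5 baseline SD, divided by the SD of change √(2(1−r)) = 1.18, 1.00, 0.77, 0.63, gives 0.42, 0.50, 0.65, 0.79 before the small-sample factor (1 − 3/167 = 0.982 at 42 df). The same benefit can therefore yield very different values until the denominator is fixed.

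**Standard error.** With an uncorrected sandwich and a normal reference, simulated type I error was 6.0 to 6.7% for the planned model and 6.7 to 7.4% for the baseline-covariate model. With the Kauermann–Carroll correction and a t reference the latter was 4.8 to 5.4%.

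**Imbalance rule.** Table 4 lists 3 contextual, 6 caregiver and 5 patient items, 14 in all. If each were tested at 0.05 (an assumption; the plan says only that they will be assessed), the chance of at least one false flag is 1 − 0.95^14 = 51% if independent and, by simulation, 36% at pairwise correlation 0.5. Nor does waiting for a flag recover the precision. At r = 0.5, adjusting for baseline QOL only when a 5% test flags it gives an empirical SD of 0.295, against 0.305 for change and 0.268 for always adjusting.

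**The case against.** The strongest reply is that the planned analysis is sound and the benefit modest. A reader might infer from the missing baseline covariate that the estimate is biased or the test invalid. The documents do not support that: allocation is randomised, so a difference in change is unbiased. Nor is the gain assured. At r = 0.8 with equal SDs the half-width falls by only about 0.015 SD, and if the SD grows at follow-up there may be no gain. That stands and limits the claim.

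A second reply concerns the remedy. Moving baseline from outcome to covariate drops participants with a baseline value only. It also removes the immediate arm's baseline-to-12-week change as a model contrast, although Aim 2 (section 2) states its hypothesis in those terms. That stands too, and is why a common baseline mean is preferred below.

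On imbalance, the second sentence already separates main from sensitivity analyses and is the more coherent reading. A reader might infer inflated type I error from the 51% figure. It shows only how readily a difference would be found at an assumed threshold; the harm is analyst discretion. Likewise, leaving out the stratum is not shown to cost precision. The protocol ties non-spousal status to higher burden, not to change in QOL, and the simulations assumed no stratum effect.

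**Conclusion.** The concern holds as one of efficiency and specification, not validity. Under equal SDs and r of 0.3 to 0.8, efficient use of baseline cuts the variance of the 12-week QOL difference by roughly 33% to 5% with 22 complete per arm, and somewhat less with 20% loss. The saving is larger if the SD shrinks (large-sample ratios 0.50 to 0.64 at k = 0.8). It is nil or slightly negative at k = 1.2 with r of 0.7 or more. Both r and k are assumptions, so the size is uncertain although the usual direction is clear. Because the effect size is this pilot's stated output, the change is worth making, along with an interval and a named denominator. The two sentences on imbalance need reconciling; that is a secondary point.

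**What to change.** For the continuous outcomes that section 7 analyses by GEE (QOL, self-efficacy, HRV):

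1. Keep the baseline, 12- and 24-week values as outcomes, but give both arms one baseline mean: terms for time, group by time at 12 and 24 weeks, no group term at baseline, and the spousal/non-spousal stratum. This keeps baseline-only participants and within-arm change. Modelling the 12- and 24-week values with baseline and baseline by time as covariates is an acceptable alternative. It estimates its own slope, so it copes better with unequal SDs, but it loses the two features just named. Choose one before the data are seen.
2. Report the 12-week difference with a 95% interval based on a small-sample-corrected standard error.
3. Compute Hedges' g as that difference divided by the pooled baseline SD, with the small-sample factor.
4. Delete the sentence "Any differences between the groups will be adjusted for further analysis" and keep imbalance-driven adjustment as a sensitivity analysis only.
5. Do not extend the model or Hedges' g to yes/no outcomes such as health-care use (Table 4), or to goal attainment without a pre-randomisation score; Table 3 places goal setting at week 1, after randomisation.

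The cost is wording and a few more lines of analysis, with no new data or visits. The downside is little or no gain, or a slight loss, if r is high or the SD grows at follow-up.

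### GEE inference on about 39 to 49 participants has no planned small-sample correction to its standard errors; uncorrected, the nominal 5% becomes roughly 6% for the 12-week contrast and 7 to 7.6% for the group-by-time test

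*Combined protocol and SAP*

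**What the plan says.** The relevant text is in Section 7 (Study Statistics) of the combined protocol and SAP.

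- **Method.** Under Aim 2, item a, for quality of life: "Generalized estimating equations (GEE) will be used to examine the difference between intervention and waitlist groups" in change from baseline to 12 and 24 weeks. The model is described as follows: "Time, group and the group by time interaction will be included in the model". Item b applies a similar approach to self-efficacy and heart rate variability.
- **Level.** The opening paragraph of Section 7: "The significance level will be set at 0.05". Sidedness is not stated.
- **Visits.** Research Variables and Measurement in Section 4: "All instruments with the exception of demographics will be measured at baseline, 12 and 24 weeks". Three visits give the interaction two degrees of freedom.
- **Numbers.** Item c, Sample Size, Aim 2: "With a target sample size of 44, 22 in the waitlist control and 22 in the intervention", and "To account for an estimated 20% attrition, we will recruit a total of 49 to the trial".
- **Role of the tests.** The same item concedes: "As a pilot study, the analyses will not have adequate power to detect significant differences". Item a compares effect sizes with clinically important improvement, "rather than placing emphasis on statistical significance".
- **Small-sample adjustment.** Item a prefers Hedges' g to Cohen's d because of bias in small samples. This is the only such adjustment in the plan. Section 7 does not state a variance estimator, working correlation, reference distribution or degrees of freedom for the GEE.

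**The concern.** The robust variance normally used with GEE is justified by a large number of independent units. Here the unit is the participant, with about 20 per arm. At that size two things go wrong in the same direction. Residuals from fitted means are too small on average, so the variance is underestimated. The normal or chi-square reference also ignores the fact that the variance was estimated.

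The plan applies small-sample reasoning to the point estimate and leaves the standard error without it. At stake are the p-values for one primary and two secondary outcomes, and any confidence intervals taken from the same models. A pilot meant to give a first effect size should describe the uncertainty around it accurately.

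**Working it through.** **Inputs from the document.** Level 0.05; target 44 (22 per arm); 49 recruited; 20% attrition, so 49 × 0.8 = 39.2, or about 39; three visits; model with time, group and their interaction.

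**Assumptions, because the plan is silent.** Two-sided Wald tests; uncorrected sandwich variance; z or chi-square reference. The closed form also assumes complete data, normal outcomes, and equal covariance and size in the two arms. For totals of 39 and 49, n = 19.5 and 24.5 stand for nearly equal arms.

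**Step 1: 12-week contrast.** Two groups by three visits with full interaction is a saturated mean model with six cell means. With complete data the contrast is the difference between arms in mean change. Its uncorrected sandwich variance is the usual two-sample variance multiplied by (n − 1)/n. The Wald statistic is therefore T × √(n/(n − 1)), with T distributed as t on 2n − 2 degrees of freedom:

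actual size = P( |t(2n − 2)| > 1.96 × √((n − 1)/n) )

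For n = 22: 1.96 × √(21/22) = 1.915, and P(|t(42)| > 1.915) = 6.23%.

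**Step 2: interaction, two degrees of freedom.** The Wald statistic is Hotelling's T² multiplied by n/(n − 1), compared with 5.991:

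actual size = P( F(2, 2n − 3) > 5.991 × ((n − 1)/n) × (2n − 3)/(2(2n − 2)) )

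For n = 22: 5.991 × (21/22) × 41/84 = 2.791, and P(F(2, 41) > 2.791) = 7.30%.

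**Step 3: interval width.** The ratio of the uncorrected to the exact half-width is 1.96 × √((n − 1)/n) divided by the 97.5% point of t(2n − 2). For n = 22: 1.915/2.018 = 0.949.

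| Total N | 12-week size | Interaction size | Width ratio, 12 weeks |
|---|---|---|---|
| 39 | 6.40% | 7.64% | 0.942 |
| 44 | 6.23% | 7.30% | 0.949 |
| 49 | 6.10% | 7.04% | 0.954 |

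Coverage of a nominal 95% interval for the 12-week contrast is thus 93.6 to 93.9%.

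**Step 4: simulation.** Null trials (12,000 to 20,000 per setting) were run at N = 39, 44 and 49. They covered independence, exchangeable and unstructured working correlations; correlation 0.5 or 0.7; no dropout, 10% then 20%, or 20% at both follow-up visits; and normal or skewed errors. These settings are assumptions. The uncorrected 12-week size was 5.9 to 6.9%, and the interaction size 6.8 to 8.1%. The maxima came from 39 participants with further 10% then 20% dropout and an unstructured working correlation. Monte Carlo error is about 0.3 to 0.5 points.

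**Step 5: when the stated 0.05 is recovered.** In the closed form, a variance with divisor n − 1 and a t reference gives exactly 5.0% for the 12-week contrast. In the simulations that included the Mancl-DeRouen variance (independence and exchangeable working correlations), the sizes were:

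| Test | z or chi-square reference | t or F reference |
|---|---|---|
| 12-week contrast | 4.9 to 5.3% | 4.3 to 4.8% (t on N − 2) |
| Interaction | 5.3 to 6.2% | 4.0 to 4.9% (F on 2 and N − 3) |

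Correcting the variance alone still leaves the interaction test slightly above 5%, so it needs the F reference as well.

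**The case against.** The strongest reply has three parts.

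**The plan does not specify an uncorrected sandwich variance.** This stands. The sentence on model terms shows no faulty choice, and an analyst could use a corrected estimator without departing from the text. A reader might infer that the trial's true significance level is above 6%. The documents do not support that as a fact; they support it only if the common uncorrected procedure is used.

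**The tests carry little weight.** This largely stands. The plan disclaims power, puts effect sizes first, defines no progression rule based on p < 0.05 and plans no interim analysis. Hedges' g is a separate calculation that already has its own small-sample correction. Section 7 also promises no confidence intervals, so their narrowness matters only if they are reported. A reader might infer that the pilot's main product is compromised, but the effect-size estimate itself is untouched. What remains is that a 0.05 level and GEE models are prespecified for three outcomes, so p-values, and probably intervals, will come from them.

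**The error is small.** This also stands: one to about three percentage points of size, and an interval 5 to 6% too narrow. A reader might infer inflation well beyond 8% for the interaction. The exact complete-data values stop at 7.6%, and the least favourable simulated setting gave 8.1%.

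**Conclusion.** The point holds in conditional form and is modest. As usually implemented, the named method does not deliver the stated 0.05 level at this sample size. With complete data the size is 6.1 to 6.4% for the 12-week contrast and 7.0 to 7.6% for the interaction. With further dropout it rises to about 7% and 8%.

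The complete-data values follow from algebra under normality and equal arms. The dropout values rest on assumed correlation, dropout pattern and working correlation. Both rest on the uncorrected variance being used with a z or chi-square reference. The direction is always toward overstated precision. This is an inexpensive improvement to the plan and does not invalidate the pilot.

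**What to change.** Add to Section 7, Aim 2, items a and b, words to this effect: GEE inference will use a small-sample corrected sandwich variance (for example Mancl-DeRouen), with a t reference on N − 2 degrees of freedom for single contrasts and an F reference on 2 and N − 3 degrees of freedom for the group-by-time test, N being the number of participants analysed. Alternatively, specify a linear mixed model with Kenward-Roger degrees of freedom. State the working correlation and that tests are two-sided.

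The cost is one or two sentences and somewhat wider intervals. With 22 per arm and complete data, the Mancl-DeRouen half-width multiplier is 2.018 × √(22/21) = 2.066. That is about 8% wider than the uncorrected 1.915 and about 2% wider than the exact 2.018. The correction is therefore slightly conservative, with size about 4 to 5%. Fixing the choice in advance also means that it cannot be made after the results are seen.
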